11.3 Description of statistical analyses

11.3.1 Overall testing strategy

The primary endpoint (ARR using confirmed relapses) will be tested using a negative binomial regression model, comparing ponesimod with placebo. The five secondary endpoints will be tested, in order as listed in Section 11.2.2, using a hierarchical testing approach. The primary null hypotheses will be tested at a two-sided 5% alpha level, and if this is rejected, the study will be declared to show conclusive evidence of efficacy.

11.3.2 Analysis of the primary efficacy variable

11.3.2.1 Hypotheses and statistical model

A generalized linear model with negative binomial distribution for the number of confirmed relapses will be assumed.

t_j denotes the length of observation for subject j
 Y_j denotes the number of relapses for subject j during t_j
 μ_j denotes the mean of the negative binomial distribution of Y_j .

The mean for the distribution of the ARR for subject j, denoted by μ_j / t_j , will be modeled by the following equation:

$$\log(\mu_j / t_j) = \mathbf{x}'_j \boldsymbol{\theta}, \text{ i.e., } \log(\mu_j) = \mathbf{x}'_j \boldsymbol{\theta} + \log(t_j), \text{ where}$$

\mathbf{x}_j is the vector denoting study treatments and covariates for subject j
 $\boldsymbol{\theta}$ is the vector of unknown fixed model parameters.

Two-sided hypotheses are expressed in terms of the model parameters $\mu_{\text{Ponesimod}}$ and μ_{Placebo} . The primary null hypothesis is that the ARR (μ) does not differ between ponesimod and placebo. The alternative hypothesis is that the ARR differs between ponesimod and placebo.

$$H_0, \text{ARR: } \mu_{\text{Ponesimod}} - \mu_{\text{Placebo}} = 0$$

vs

$$H_1, \text{ARR: } \mu_{\text{Ponesimod}} - \mu_{\text{Placebo}} \neq 0$$

The null hypothesis will be tested by a two-sided Wald test within the negative binomial regression model [see Section 11.3.2.3], with a two-sided significance level of 0.05.

11.3.2.2 Handling of missing data

11.3.2.2.1 Main analysis of the primary endpoint

All confirmed relapses from randomization up to the EOS visit for subjects in the FAS will be used in the main analysis of the primary endpoint regardless of study drug compliance, therefore no data will be excluded from the analysis. No missing data imputation is used for the main analysis of the primary analysis.

Every effort will be made to collect as complete relapse information as possible, with a focus on collecting all start dates and all EDSS/FS data required for the relapses to make a correct evaluation of relapse confirmation. All relapses with missing or incomplete start dates will be included in the primary efficacy analysis, unless it is clear that they have occurred prior to randomization.

11.3.2.2.2 Sensitivity analysis of the primary endpoint

Missing data will be assessed in a number of ways to test the robustness of the primary endpoint results and to ensure that selection bias / informative drop-outs have not had an influence on the results.

New or Worsening Neurological Symptoms Considered as Relapses:

New or worsening neurological symptoms are reported via a telephone interview or at the site in a face-to-face interview and at both these stages a decision must be taken by the

treating neurologist to refer the subject to the efficacy assessor. Only at this point is the symptom considered a relapse and is assessed for confirmation. To ensure no bias in the selection of symptoms considered as relapses between treatments, an analysis will compare the proportion of these new or worsening neurological symptoms that are considered as relapses and as confirmed relapses. If there is an imbalance in the selection between treatments, this will be explored further.

Early Study Withdrawal:

To assess the impact of subjects withdrawing from the study prior to the Study Closure (60 weeks after the last subject is randomized or Week 156) a number of sensitivity analyses will be performed. These include the imputation of confirmed relapses using various assumptions for the period with missing data. The proportion of missing data will be calculated as

$$1 - \frac{\text{cumulative time between randomization and EOS}}{\text{cumulative time between randomization and Study Closure or Week 156}}$$

A worst case imputation will impute the observed ARR for ponesimod subjects up to EOS during the period EOS up to Study Closure and impute 0 relapses for placebo subjects during this period. A second imputation method will impute the observed placebo ARR up to EOS for the period EOS up to SC for both treatments, using simulations and bootstrapping techniques to calculate the 95% CI. A third more conservative approach will impute the observed individual treatment ARR up to EOS for the period EOS up to SC in a similar manner.

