3.5.3.2 Post-treatment observation period

Subjects who prematurely discontinue study drug and complete the 30-day safety follow-up including the FU visit, will enter the PTOP which lasts until 60 weeks after randomization of the last subject or until Week 156, whichever is first (i.e., planned EOT visit) irrespective of treatment completion. It consists of an abbreviated schedule of assessments at the time of the originally scheduled 12-weekly visits. The aim is to

follow-up with the subjects after discontinuation of study treatment and to collect long-term data while the subject possibly receives other approved MS therapies.

While participating in the PTOP, subjects may not be enrolled in another clinical trial. They may, however, withdraw their consent to participate to this study at any time [see Section 9.2].

3.5.3.3 *End-of-Study*

[figure not shown]
The study level EOS will occur after all subjects have completed the safety FU period or the last visit of the PTOP.

For an individual subject, EOS is reached when treatment, post-treatment safety FU, and if applicable, the PTOPs have been completed:

- For subjects who complete the treatment period, and for subjects who prematurely discontinue study treatment and do not enter the PTOP, the EOS visit corresponds to the 30-day FU visit (FU).
- For subjects who prematurely discontinue study treatment and enter the PTOP period, the EOS visit corresponds to the last visit of the PTOP.

The overall study design is shown in [Figure 1](#).

Figure 1 AC-058B302 study design

D = day; DMF = dimethyl fumarate; EOS = End-of-Study; EOT = End-of-Treatment; FU = follow-up; V = visit; W = week; *Lymphocyte tests every 4 weeks (\pm 3 days) until Week 24; ** Subjects participating in the lymphocyte subset sub-study will have an additional FU visit approximately 7 days after the last dose of study drug (FU7d).

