11.5.1 Primary endpoint

The sample size for the study was determined by a simulation using the negative binomial distribution. A sample size of 600 subjects (300 per treatment group) will provide a power of approximately 90% for a significance level of 0.05, under the assumption that the ARR (for confirmed relapses up to EOS) is 0.50 for placebo and 0.325 for ponesimod (which corresponds to a risk reduction of 35%), and using a dispersion $k = 1.3$ (where the variance is $= \mu + k \mu^2$). A mean subject follow-up of 1.9 years is assumed with 3.3 years maximum follow-up.

The dispersion from the ponesimod Phase 2 study was 1.0; a higher dispersion is assumed here due to the potentially higher disease activity in this subject population.

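### Early-withdrawal sensitivity analyses (Protocol 11.3.2.2.2): the method called more conservative is the least conservative of the three, the missing-time formula understates missingness, and 'worst case' is a loose label

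*Protocol*

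**What the plan says.** Section 11.3.2.2.2 of the protocol addresses subjects who leave the study before Study Closure (60 weeks after the last randomization, or Week 156). It fixes two things.

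**Three imputations** for the period from EOS to Study Closure:
- Method 1: "A worst case imputation will impute the observed ARR for ponesimod subjects up to EOS", with no relapses imputed for placebo subjects.
- Method 2: the observed placebo ARR in both arms, with simulation and bootstrapping for the confidence interval.
- Method 3: "A third more conservative approach will impute the observed individual treatment ARR up to EOS", handled in a similar manner.

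**A missing-data proportion**: one minus a ratio. The numerator is cumulative time from randomization to EOS. The denominator is "cumulative time between randomization and Study Closure or Week 156".

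Section 3.5.3.3 defines EOS. For subjects who complete treatment, "the EOS visit corresponds to the 30-day FU visit (FU". Section 8.3.1.2 places that visit 30 to 37 days after the last dose. Section 3.5.5 allows the EOT visit up to 4 weeks after closure is announced.

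**The concern.** The stated purpose of these analyses is to show that informative dropout has not driven the primary result. Each label tells the reader how hard the result was tested. If the method described as more conservative keeps the full treatment effect in the missing time, agreement with the main analysis is close to automatic and says nothing about informative dropout. If the formula lets completers count for more than their planned time, the report quotes too little missing primary-endpoint time. If the worst case lets ponesimod withdrawals keep the treated relapse rate, its name promises more than it delivers.

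**Working it through.** **Inputs from the protocol.** Section 11.5.1: ARR 0.50 (placebo) and 0.325 (ponesimod), dispersion k = 1.3, 300 per arm, mean follow-up 1.9 years. Section 11.3.2.1: two-sided 0.05. Visit timing: Sections 3.5.3.3, 3.5.5 and 8.3.1.2.

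**The plan's own figure first.** Section 11.5.1 states: "A sample size of 600 subjects (300 per treatment group) will provide a power of approximately 90% for a significance level of 0.05". With the negative binomial Wald approximation, Var(log RR) = [1/(0.50 × 1.9) + 1/(0.325 × 1.9) + 2 × 1.3]/300, so SE = 0.1326. Power = Φ(|ln 0.65|/0.1326 − 1.96) = 90.1%. The figure reproduces, as do all nine rows of the table in Section 11.5.3, each within 0.1 point.

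**Imputation methods.** Let c = 0.50 and p = 0.325. Let m_p and m_c be the shares of planned time missing on ponesimod and placebo. The protocol gives no dropout rate, so these shares are assumptions. Expected rate ratios over the full planned time:
- Method 1 ('worst case'): p / [c(1 − m_c)]
- Method 2 (placebo rate in both arms): [p(1 − m_p) + c·m_p] / c
- Method 3 (own arm): p / c
- Harsher case (placebo rate for ponesimod, 0 for placebo): [p(1 − m_p) + c·m_p] / [c(1 − m_c)]

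| Missing, both arms | Method 3 | Method 2 | Method 1 | Harsher case |
|---|---|---|---|---|
| 5% | 0.650 | 0.667 | 0.684 | 0.703 |
| 10% | 0.650 | 0.685 | 0.722 | 0.761 |
| 20% | 0.650 | 0.720 | 0.812 | 0.900 |

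(0.6675 and 0.8125 are shown as 0.667 and 0.812.)

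Method 3 contains neither m_p nor m_c, so it stays at 0.650 for any missingness, equal or not. Method 1 raises the ratio whenever placebo time is missing. Method 2 raises it whenever ponesimod time is missing and p < c.

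A simulation of 250 trials with 10% of time missing agrees. Mean rate ratios were 0.655 with no imputation, 0.654 (method 3), 0.692 (method 2), 0.728 (method 1) and 0.766 (harsher case).

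With unequal missingness, 15% on ponesimod and 5% on placebo, method 1 gives 0.325/(0.50 × 0.95) = 0.684 and method 2 gives (0.325 × 0.85 + 0.50 × 0.15)/0.50 = 0.703. Method 2 is then the harsher. The crossover lies at ponesimod missingness about twice that of placebo.

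**Missing-data formula.** Assume a mean planned time of 1.9 × 365.25 = 694 days, a fraction d of subjects withdrawing, each losing half the planned time, and every completer running o days past the denominator's end point. The true missing share is 0.5d. The formula returns 0.5d − (1 − d)·o/694. The overruns tried are 30 and 37 days (FU window) and 65 days (4 weeks to EOT plus 37 days).

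| Withdrawn | True missing | o = 30 | o = 37 | o = 65 |
|---|---|---|---|---|
| 0% | 0% | −4.3% | −5.3% | −9.4% |
| 10% | 5.0% | 1.1% | 0.2% | −3.4% |
| 20% | 10.0% | 6.5% | 5.7% | 2.5% |
| 30% | 15.0% | 12.0% | 11.3% | 8.4% |

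The shortfall runs from about 3 to 9 percentage points. Capping each subject's numerator at Study Closure or Week 156 restores the true values.

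**The case against.** **The operations are explicit.** A reader of the report can see what was imputed, so 'more conservative' is a wrong adjective and not a wrong method. That is fair, but the adjective says how strong the evidence is, and it points the wrong way. One could read the third method as using each subject's own rate. The natural reading is arm-specific, and nothing in the other reading would make it more conservative than imputing the placebo rate.

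**The worst case is already the harshest planned analysis.** This stands when missingness is similar in both arms. Method 2 already gives ponesimod withdrawals the placebo rate; only the combination with zero relapses on placebo is absent. A reader might infer that the worst case is milder than its companions. The documents support that only if ponesimod missingness is about twice placebo's or more. A harsher scenario can always be built, so this is a point about the name.

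**The formula feeds nothing.** It sets no imputed count, test or decision. A reader might infer that the overrun distorts the imputations. It does not: they cover EOS to Study Closure, an empty interval for completers. If the sums were restricted to early withdrawals the overrun would vanish, but the text states no such restriction and the all-subject reading is the natural one.

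**The list is open.** Section 11.3.2.4 leaves further sensitivity analyses to the SAP, so the lack of a tipping-point analysis is not a defect.

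**Missing time may be small.** Subjects who stop study drug remain under observation in the PTOP, so only study withdrawal creates it. That limits the size of the imputation effects and leaves their direction unchanged.

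**Conclusion.** Two statements are wrong as written, and one label is loose.

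1. Method 3 is the least conservative of the three whenever the observed ponesimod ARR is below placebo. This does not depend on the amount of missing data.
2. Summed over all subjects, the missing-data proportion is too low and can be negative: about −4.3% with no dropout and a 30-day overrun. The 3 to 9 point range rests on the assumed 694-day mean, a half-time loss per withdrawal, and overruns of 30 to 65 days.
3. The worst case is the harshest listed method under similar missingness, but not a true worst case. The gap to the harsher rule is 0.019, 0.039 and 0.088 on the rate ratio at 5%, 10% and 20% missing. These shares are assumptions.

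It would be tempting to conclude that the primary result or the sample size is compromised. The documents do not support that: the main analysis uses no imputation (Section 11.3.2.2.1), and the 90% power reproduces.

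**What to change.** - Drop 'more conservative' from the third method and call it the own-arm (missing-at-random) reference.
- In the missing-data proportion, cap each subject's numerator at the earlier of EOS and the Study Closure or Week 156 date used in the denominator, and say that the sums run over all subjects.
- Either rename the worst case, or redefine it so that ponesimod withdrawals receive at least the observed placebo ARR and placebo withdrawals receive 0. A tipping-point analysis that raises the imputed ponesimod rate until significance is lost is an optional addition.

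The cost is a few changes of wording and a few lines of programming, to be made before unblinding. No extra data are needed. The reported missing share will be higher, and a redefined worst case would give a less favourable rate ratio.

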11.3.2.3 Main analysis

The primary statistical analysis will be performed on the FAS using the model described in Section 11.3.2.1 for confirmed relapses, with the stratification variable EDSS category included as covariate in the model and the logarithm of time on treatment up to EOS as an offset variable. The effect size will be measured by the relative reduction in the model estimated mean ARR for ponesimod compared to placebo including two-sided 95% Wald CIs.

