4.2 Rationale for the selection of the study population

RMS is the most frequent presentation of MS. Despite multiple therapies available, many subjects continue to experience relapses and accumulate disability.

Subjects with SPMS represent a significant unmet medical need for new therapeutic options. According to the US label [[Tecfidera USPI](#)], these subjects can also be treated with Tecfidera[®], but they have generally been less studied and have often not been included in pivotal trials of medications approved for the treatment of RMS. For these reasons, it is important to also evaluate the benefit/risk profile of ponesimod in subjects who are treated with Tecfidera[®] and have SPMS with superimposed relapses.

The clinical relevance of McDonald 2010 Diagnostic Criteria, including subjects with only one attack, in the presence of supplementary clinical and/or MRI criteria as well as the value of early treatment in MS is widely recognized.

The study will enroll subjects treated with DMF with recent evidence of active disease as determined by clinical or imaging criteria. Inclusion criteria for active disease consist of prognostic factors that identify patients not responding satisfactorily to treatment, and thus require more efficacious therapies. The requirement for at least 6 months of DMF treatment prior to study entry aims to ensure:

- A better adherence to treatment during the study as most of flushing and gastrointestinal AEs which lead usually to treatment discontinuation occur during the initial months following DMF treatment,
- the evaluation of patient's response to DMF treatment occurs at an appropriate time to avoid delaying additional treatment or a change in treatment,
- most of the effect of DMF on lymphocyte counts is established.

Furthermore, the requirement for imaging or clinical signs of disease activity after at least 3 months of DMF treatment is to ensure additional treatment is justified [see Section [3.2](#)].

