4.3 Inclusion criteria

For inclusion in the study, all of the following inclusion criteria must be fulfilled. It is not permitted to waive any of the criteria for any subject:

1. Signed informed consent prior to initiation of any study-mandated procedure.
2. Males and females aged 18 to 55 years (inclusive).
3. A woman of childbearing potential (WOCBP) is eligible only if the following applies:
 - must have a negative serum pregnancy test at Visit 1 (Screening) and a negative urine pregnancy test at Visit 2 (Baseline);
 - must agree to undertake monthly urine pregnancy tests during the study and up to 30 days after study treatment discontinuation;
 - must use reliable methods of contraception until 30 days after study treatment discontinuation as described in Section 4.5.2;

Definition of WOCBP and the acceptable methods of contraception for this study are described in Section 4.5.

4. Presenting with a diagnosis of MS as defined by the revised (2010) McDonald Diagnostic Criteria for MS [see [Appendix 2](#)] with relapsing course from onset (i.e., RRMS, or SPMS with superimposed relapses).
5. Ongoing treatment with DMF for at least 6 months prior to Visit 1 (Screening).
6. Active disease after at least 3 months of DMF treatment defined by at least one of the following features:
 - At least one MS attack supported by objective neurological examination with onset within 12 months to 1 month prior to baseline EDSS assessment;
 - At least one Gd+ lesion on an MRI of the brain or spinal cord, performed either within 12 months prior to Visit 1 (Screening) or during the pre-randomization period (MRI assessed at Visit 2 [Baseline] may be the qualifying scan);
 - Presence of at least one new or one unequivocally enlarging T2 lesion on an MRI of the brain or spinal cord, assessed by comparing two MRI scans: the first MRI scan must be performed within 15 months prior to Visit 1 (Screening) and after at least 3 months of DMF treatment; the second MRI scan must be performed prior to randomization (MRI assessed at Visit 2 [Baseline] may be used). The presence of at least one new or one unequivocally enlarging T2 lesion has to be confirmed by the MRI central reading facility prior to randomization.
7. Ambulatory and with an EDSS score between 0 and 6.0 (inclusive) at Visit 1 (Screening) and Visit 2 (Baseline).
8. For subjects with ongoing treatment with DMF \geq 12 months prior to screening:

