4.6.2 MS history

MS disease characteristics, as defined below and evidenced by documentation in the patient charts, will be recorded on the MS history page of the eCRF:

- Date of first known MS symptoms;
- Date of MS diagnosis;
- MS type (e.g., RRMS, SPMS);

- Symptoms associated with MS (e.g., optic neuritis, numbness, spasticity, tremor, fatigue, dizziness, dysfunctional bladder, cognitive problems, etc.) within the last 24 months prior to the study;
- Number of documented MS relapses within the last 12 months and between 12 and 24 months prior to the study. The onset date and the duration of the relapse when available, and treatment of these relapses (corticosteroids, ACTH, plasmapheresis etc.) will be reported;
- Number of documented Gd+ lesions per scan and number of documented T2 hyperintense lesions per scan on any MRI scan performed within 24 months prior to the study. Additionally, the condition of the MRI scan will be collected (e.g., scanner type, manufacturer and strength, the type of T1 sequence and number of slices used to detect Gd+, contrast agent used [Gd type], dose of contrast agent and time of injection, time of T1 sequence, the type of T2 sequence and number of slices used to detect T2 hyperintense lesions);
- Previous MS disease-modifying treatments received at any time in the past. For treatments received in the last 24 months prior to the study, start date, end date, dose, route, frequency, and reason for discontinuation will be recorded in the previous/concomitant medication page of the eCRF [see Section 5.2.2].

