11.3.2.4 Supportive/sensitivity analyses

The main supportive analysis will count all confirmed relapses up to EOT + 30 days using the FAS. In addition to the missing data sensitivity analysis described in Section 11.3.2.2, the following sensitivity analyses (based on the FAS, if not otherwise stated) are planned using the model described in Section 11.3.2.1:

- Analysis with treatment as the only covariate in the model for all confirmed relapses up to EOS and up to EOT +30 days;
- Analysis adjusting for the stratification covariate using the actual EDSS recorded at baseline on the eCRF up to EOS and up to EOT + 30 days;

- Analysis adjusting for additional baseline characteristics up to EOS and EOT + 30 days;
- Analysis counting only confirmed relapses up to starting alternative MS treatments or EOS for subjects not switching;
- Analyses using different methods of relapse imputation between EOT + 30 days and EOS (PTOP) to further assess the impact of switching to alternative MS treatments;
- Analyses based on the PPS counting confirmed relapses up to EOS;
- Analysis using all relapses (confirmed or unconfirmed) up to EOS and EOT + 30 days;

Further sensitivity analyses will be described in the SAP.

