11.3.2.5 Subgroup analyses

The ARR within each level of each subgroup will be analyzed using an unadjusted negative binomial model. Subgroups of interest (including the stratification factor) are:

- Baseline EDSS ($\leq 3.5, > 3.5$);
- MS subtype (relapsing remitting, secondary progressive);
- Gender (male, female);
- Age ($< 40, \geq 40$);
- Prior MS treatment other than DMF (yes, no);
- Relapse in the previous 6 month prior to study entry while on treatment with DMF ($\leq 1, \geq 2$);
- Gd+ T1 lesions at baseline (absent, present);

Further subgroup analyses might be performed using other baseline characteristics and other variables. The analyses including interaction tests will be specified in more detail in the SAP.

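### The primary relapse-rate model adjusts only for EDSS category and leaves out the prior-relapse count recorded at entry, giving up some precision

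*Protocol*

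**What the plan says.** Protocol 11.3.2.3 specifies the main analysis of confirmed relapses as a negative binomial regression on the full analysis set, "with the stratification variable EDSS category included as covariate in the model" and log time as the offset. The synopsis says the same. The test is a two-sided Wald test "with a two-sided significance level of 0.05" (11.3.2.1).

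Four other places bear on the choice of covariates:

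- 4.6.2 requires this item on the MS history page: "Number of documented MS relapses within the last 12 months and between 12 and 24 months prior to the study".
- 4.2 says: "Inclusion criteria for active disease consist of prognostic factors that identify patients not responding satisfactorily to treatment". One of the three alternative criteria in 4.3 is "At least one MS attack supported by objective neurological examination with onset within 12 months to 1 month prior to baseline EDSS assessment". The other two are MRI criteria, so a subject can enter with no recent relapse and the count will vary.
- 11.3.2.4 lists, among the sensitivity analyses, "Analysis adjusting for additional baseline characteristics up to EOS and EOT + 30 days", without naming the characteristics.
- 11.3.2.5 lists as a subgroup factor "Relapse in the previous 6 month prior to study entry while on treatment with DMF", split at one or fewer against two or more.

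The sample size in 11.5.1 assumes dispersion k = 1.3, against 1.0 in Phase 2, because "a higher dispersion is assumed here due to the potentially higher disease activity in this subject population".

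**The concern.** Dispersion is the between-subject variation in relapse rate that the model leaves unexplained, and it is about half of the variance of the primary estimate under the design assumptions. A baseline variable that predicts relapse moves part of that variation into the explained part of the model. The standard error of the treatment effect then falls without enrolling anyone.

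The number of past relapses is an obvious candidate. It is measured before randomization, it is already collected, and it is the same kind of event as the endpoint. The covariate set of the primary test is fixed in the protocol itself, so an adjusted sensitivity analysis cannot improve that test. With no interim analysis (11.4) and no sample-size re-estimation (11.5.4), power lost to poor assumptions cannot be recovered later.

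**Working it through.** **Inputs (11.5.1, 5.1.3, 11.3.2.1).** 300 subjects per arm, 1:1; ARR 0.50 for placebo and 0.325 for ponesimod (rate ratio 0.65); k = 1.3; mean follow-up t = 1.9 years; two-sided alpha 0.05.

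**Step 1: reproduce the stated power.** For the log rate ratio,

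Var = [1/(r0·t) + 1/(r1·t) + 2k] / n, and power = Φ(|log RR|/SE − 1.96).

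- 1/(0.50 × 1.9) = 1.053; 1/(0.325 × 1.9) = 1.619; 2k = 2.6; sum 5.272.
- SE = √(5.272/300) = 0.1326; |log 0.65| = 0.4308.
- Power = Φ(0.4308/0.1326 − 1.96) = 90.1%, against about 90% stated.

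The formula also reproduces all nine rows of the table in 11.5.3 to within 0.1 point. The dispersion term is 2.6/5.272 = 49% of the variance.

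**Step 2: lower the residual dispersion.** The protocol does not give the share of k that prior relapses explain, so the share is an assumption and is shown as a range.

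| Share of k explained | Residual k | SE | Power | CI narrower by | n per arm for the same 90.1% |
|---|---|---|---|---|---|
| 0% | 1.30 | 0.1326 | 90.1% | 0% | 300 |
| 10% | 1.17 | 0.1293 | 91.5% | 2.5% | 286 |
| 20% | 1.04 | 0.1259 | 92.8% | 5.1% | 271 |
| 30% | 0.91 | 0.1224 | 94.1% | 7.7% | 256 |

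The gain is larger in the less favourable scenarios that 11.5.3 tabulates. For the same four shares, power is 77.7%, 79.7%, 81.8% and 84.0% with a 30% reduction, and 82.3%, 84.6%, 86.8% and 89.1% with k = 2.0.

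**Step 3: check by simulating the fitted models.** Assumptions: prior-year count roughly Poisson with mean 1 (capped at 4), total dispersion 1.3, follow-up uniform on 0.8 to 3.0 years, EDSS not modelled, 1,500 runs per scenario.

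| Rate multiplier per prior relapse | Mean SE without / with the count | Power without / with the count |
|---|---|---|
| 1.00 (no association) | 0.1344 / 0.1344 | 89.0% / 89.3% |
| 1.22 | 0.1337 / 0.1326 | 89.8% / 89.9% |
| 1.35 | 0.1323 / 0.1296 | 90.9% / 92.1% |
| 1.49 | 0.1309 / 0.1256 | 90.7% / 92.0% |

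The estimated rate ratio lay between 0.646 and 0.650 in every fit, so adjustment did not change what is estimated. Under the null, rejection was 6.1% in both models with no association, and 4.9% without against 4.2% with the count at multiplier 1.35 (Monte Carlo standard error about 0.6 points). There is no sign that adjustment inflates type I error.

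The simulated SE reductions (0.8%, 2.0% and 4.0%) are smaller than the formula gives for similar shares. Part of the reason is that the unadjusted fits already returned a dispersion below 1.3 (1.26, 1.21 and 1.16). The formula figures are therefore the more generous of the two.

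**The case against.** The strongest reply is that nothing here is defective. The model adjusts for the only stratification factor, the stated power is correct, the sponsor planned above its Phase 2 dispersion, and 11.5.3 already shows power at k = 2.0. All of that stands, and it limits the point to efficiency.

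The benefit may also be small. Section 1.5 says that disease activity varies over time within a subject and that placebo-arm relapse rates fall well below pre-trial rates. Subjects need only six months of DMF before screening (4.3), so a longer look-back can mix relapses before and during DMF. What 4.2 calls prognostic is the set of activity criteria, not the count as such. This is why the gain is given as a range starting at zero and why a 12-month window is preferable to 24 months.

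Nor is the change purely clerical. The counts are historical and limited to documented relapses, 13.6 requires a written amendment, and two earlier amendments answered comments from a special protocol assessment.

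Three stronger readings are tempting but unsupported:

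- A reader might infer that the latest amendment created a mixed population by opening an MRI-only route. The amendment rationale says a Gd+ lesion already qualified a subject. The amendment added the T2 criterion and allowed the pre-randomization scan, and the sponsor states that the population does not change.
- A reader might infer that prior relapse is hidden among the unnamed covariates of 11.3.2.4. It is a named subgroup factor in 11.3.2.5, and listing sensitivity covariates is normal content for the analysis plan.
- A reader might hope for power near 99%. With the formula above, that needs residual k near 0.18, or about 86% of 1.3 explained (1 − 0.18/1.3). Nothing in the protocol suggests this.

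**Conclusion.** The point holds as a recommendation to improve efficiency. The primary test is valid, and the 90% power claim is right under its own assumptions. Omitting the prior-relapse count gives up between nothing and about 4 percentage points of power, and between 0% and about 8% of confidence interval width, if the count explains 0% to 30% of the assumed dispersion. That share is an assumption. The simulation, under its own assumed associations, gave gains of 0.1 to 1.3 points. If past relapses do not predict future ones, adjustment neither helps nor does visible harm: the standard error was unchanged in that case.

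**What to change.** In 11.3.2.3 and the matching synopsis text, before unblinding, add the number of documented relapses in the 12 months before study entry to the primary model beside EDSS category. Fix one form, for example 0, 1, and 2 or more, and state one rule for missing counts. Keep the EDSS-only model as a named sensitivity analysis so that the effect of the change is visible.

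No new data collection is needed, since 4.6.2 already requires the count. The cost is a small protocol amendment, with notification of the regulator because the protocol went through special protocol assessment. The remaining risk is that there is little or no gain if past relapses predict poorly.
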